#### Dose Escalation

Following commencement of study treatment, patients are evaluated for response after 8 weeks and, if the patient has required one or more RBC transfusion in that period then the dose is increased by one dose level. After each dose adjustment, the patient remains on the dose level for a minimum of 8 weeks before further adjustment is permitted.

With the exception that the starting dose will be maintained if an erythroid response (defined as a 50% reduction in pRBC from baseline) is seen after the initial 8 weeks of dosing. A re-assessment will be done for these patients at week 12 and if transfusion independence (TI) is observed the dose will not be increased. If TI is NOT observed at this point, the dose will be increased by one dose level.

## Dose Reduction

The down titration of the study treatment is allowed at any time but must be performed if any of the following criteria are met. Hb levels should be retested for confirmation every 2 weeks after a dose reduction, however it is per investigator's discretion:

- a) Transfusion independent for  $\geq 56$  days consecutively and Hb  $\geq 12$  g/dL; or
- b) Transfusion independent for  $\geq 56$  days consecutively and the rate of rise of Hb  $\geq 2.5$  g/dL over 4 weeks.
- c) In the instance where the patient achieved TI in the initial 8-weeks of the study, or has undergone treatment with the maximum allowable dose, i.e., 400 mg TIW or 3.5 mg/kg for at least 8-weeks, patient may undergo dose reduction by 1-dose level. If there were no difference in erythroid response (same transfusion burden and Hb was unchanged) at this dose level for 8-weeks compared to another lower dose level, investigator may contact Sponsor's Medical Monitor to discuss another potential dose reduction.

This is an effort to treat patients with the lowest effective dose needed to maintain erythroid response; thus, study drug dose can be increased again if erythroid response appeared to be decreased with dose decrease.

Reduction should be to one dose level lower than the dose at which the subject is receiving.

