Study Design Overview (cont.):	
standard site transfusion criteria will be documented in overall study files.
 
For all patients (OL and DB components), dose adjustments/escalations will occur every 8 weeks at pre-defined dose level increments, with the exception that the starting dose will be maintained if an erythroid response (defined as a 50% reduction in pRBC transfusion from baseline) is seen after the initial 8 weeks of dosing. A re-assessment will be done for these patients at week 12 and if transfusion independence (TI) is observed the dose will not be increased. If TI is NOT observed at this point, the dose will be increased by one dose level. See Appendix C for details on dosing and dose escalation.
 
Once TI for at least 8 continuous weeks has been achieved, Maintenance Phase will begin and the study drug dose should follow guidance described in Appendix D.
 
During the course of the study, visits and assessments will be performed as defined in the schedule of assessments (see Appendix A and Appendix B).
 
The overall study duration is 52 weeks with primary efficacy assessment after the first 28 weeks in the DB component, and continued treatment up to 52 weeks.
 
The OL portion patients who receive roxadustat may remain in the study up to 52 weeks of treatment based on investigator discretion, adequate safety, and impression of benefit. These patients will undergo all procedures as the randomized patients in the DB study with the exception of not completing the Health-related quality of life (HRQoL) questionnaires.
 
When all the randomized (DB) patients complete 28 weeks of treatment or are discontinued from study medication before this time, the analysis of the primary and secondary efficacy endpoints will occur. Only Sponsor personnel who are not directly involved with the study sites/patients will have access to the unblinded data. The blind will be maintained for study patients, PI, site staff and site monitoring personnel for the remainder of the study (to Week 52 plus a 4 week follow-up period).
 
Follow-Up:
 
All patients who complete 52 weeks (of treatment with study medication) will undergo a 4 week follow-up period after the last dose of study medication.
 
Patients who discontinue study medication early (for any reason) will remain in the study through the entire 52 week study period. Patients will have a 4 week follow-up visit after stopping study medication and then be followed up at a reduced visit schedule of every 8 weeks

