## 2.5 Roxadustat Dose Rationale

For the treatment of anemia in MDS patients, roxadustat will be administered orally three times per week (TIW) and titrated to achieve the target response. It is expected that patients will require a higher dose due to bone marrow dysfunction and this is supported by experience with the earlier agent FG-2216 as discussed in [Section 2.4.2](#). The OL component will evaluate three cohorts (approximately 1.5 mg/kg, 2.0 mg/kg and 2.5 mg/kg) to optimize the starting dose for the DB component. After each 8 weeks on a dose level, the patient's response will be assessed and the study treatment will be titrated (pre-defined levels, [Appendix C](#)) to achieve transfusion independence. The study treatment can be down titrated at any time. Once the patient has achieved TI, the dose will be maintained as per [Appendix D](#). The regimen is consistent with that of the roxadustat CKD clinical development program and utilizes tiered body weight. The maximum permitted dose will be the same as that allowed in the CKD program of 400 mg or 3.5 mg/kg TIW (whichever is lower).

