**Figure 3 Study Schemas**

Up to 24 patients will be enrolled in sequential dose level cohorts prior to start of the DB component of the study. All patients will receive roxadustat in an OL manner. The first 8 patients will receive a starting dose of 1.5 mg/kg (Dose Level 1). The next 8 patients will receive a starting dose of 2.0 mg/kg (Dose Level 2). The last 8 patients will receive a starting dose of 2.5 mg/kg (Dose Level 3). Each patient's starting dose will be determined by their actual weight at the registration/randomization visit. The roxadustat dose per body weight are estimates only and the exact dose will be assigned per body weight ranges as shown in the body of the protocol.

The OL component is intended to optimize the starting dose for the subsequent double-blind component of the study in which 160 eligible lower risk MDS patients with LTB will be randomized 3:2 to roxadustat or matching placebo. It is anticipated that the starting dose level

will be level 2 (2.0 mg/kg) and the protocol is written to reflect this but if the OL data suggests a lower (1.5 mg/kg) or a higher (2.5 mg/kg) dose to be a more optimal starting dose, then this will be implemented accordingly.

Patients in the DB component of the study will be randomized with the following stratifications:

- Serum EPO level: either  $\leq 200$  mIU/mL OR  $> 200$  mIU/mL and  $\leq 400$  mIU/mL
- IPSS-R low risk / very low risk vs. intermediate risk group classification
- RBC transfusion burden: 1 pRBC/8-weeks over 16 consecutive weeks vs 2-4 pRBC/8-weeks

For the OL and the DB components, dose adjustments/escalations will occur every 8 weeks at pre-defined dose level increments, with the exception that the starting dose will be maintained if an erythroid response (defined as a 50% reduction in pRBC from baseline) is seen after the initial 8 weeks of dosing. A re-assessment will be done for these patients at week 12 and if transfusion independence (TI) is observed the dose will not be increased. If TI is NOT observed at this point, the dose will be increased by one dose level. See [Appendix C](#) for details on dosing and dose adjustment.

Once transfusion independence for at least 8 continuous weeks has been achieved and the “maintenance treatment period” starts, the study drug dose should follow guidance described in [Appendix D](#).

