### 3.3.2 Dose Adjustment

There are two periods for the study drug dosing – the correction phase and the maintenance phase.

**Correction phase:** Dose adjustments/escalations will occur every 8 weeks at pre-defined dose level increments, with the exception that starting dose will be maintained if erythroid response (defined as a 50% reduction in pRBC from baseline) is seen after the initial 8 weeks of dosing. A re-assessment will be done for these patients at week 12 and if transfusion independence (TI) is observed the dose will not be increased. If TI is NOT observed at this point, the dose will be increased by one dose level (see [Appendix C](#)).

**Maintenance Phase:** Once transfusion independence for at least 8 continuous weeks ( $\geq 56$  consecutive days) has been achieved and the “maintenance treatment period” starts, the study drug dose may be escalated or reduced in pre-defined levels as described in [Appendix D](#).

During the course of the study, visits and assessments will be performed as defined in the schedule of assessments (see [Appendix A](#)).

Dose reductions can occur at any time per defined criteria (see [Appendix C](#) and [Appendix D](#)).

Dosing with study medication may be held (not given) for one single instance not to exceed 2 weeks. Please contact the medical monitor with any questions.

Given the complexities of the dose adjustment algorithm, and the need to take into consideration various clinical parameters, it is not considered a protocol deviation when study subjects are dosed based on their clinical circumstance, whether or not this is concordant with the roxadustat

dosing algorithm, unless it is related to “excessive hematopoiesis” or “Overdose” (prescribed 400 mg or > 3.5 mg/kg/dose).

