### Appendix C – Dose Adjustment Rules During the Titration to Achieve TI – Correction Phase (Prior to Maintenance Phase)

Dose adjustment will follow as described in the table below. The down titration of the dose is allowed at any time. The maximum dose of study medication is capped at 3.5 mg/kg per dose or 400 mg, whichever is lower.

In the OL component, cohort 1 (n=8) starts at 1.5 mg/kg, (Dose Level 1) followed by cohort 2 (n=8) at 2.0 mg/kg (Dose Level 2) and finally cohort 3 (n=8) at 2.5 mg/kg (Dose Level 3). The optimal starting dose will be selected for the DB component following evaluation of the OL data. It is anticipated that for the DB component, the starting dose level will be level 2 (2.0 mg/kg) and the protocol is written to reflect this but if the OL data identifies level 1 or 3 as a more optimal starting dose, this will be implemented.

Body Weight	Dose Levels					
	approx. 1.0 mg/kg	approx. 1.5 mg/kg	approx. 2.0 mg/kg	approx. 2.5 mg/kg	approx. 3.0 mg/kg	approx. 3.5 mg/kg
45 - <70 kg	50 mg TIW	70 mg TIW	100 mg TIW	150 mg TIW	200 mg TIW*	250 mg TIW*
70-100 kg	100 mg TIW	120 mg TIW	150 mg TIW	200 mg TIW	250 mg TIW	300 mg TIW*
>100 kg	120 mg TIW	150 mg TIW	200 mg TIW	250 mg TIW	300 mg TIW	350 mg TIW **

\* Patients body weight MAY require a lower dose than listed in the table above, due to the potential for the maximum dose being exceeded. The next dose given should be at one dose level immediately below what is in the above table. In some cases, a dose escalation will NOT be allowed.

\*\* Patients with body weight  $\geq$  120 kg will receive fixed dose of 400 mg TIW at Dose Level 3.

If there is **ANY** question as to the appropriate dose to administer contact the CRA or medical monitor for guidance.

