### Appendix D - Dose Adjustment Rules for Patients who have TI for $\geq 56$ Days (8 weeks) – Maintenance Phase

A modified dose adjustment algorithm will apply to patients who have attained TI  $\geq 56$  days. The down titration of the dose is allowed at any time.

Change in Hb from 4 weeks earlier (g/dL)	Hemoglobin (Hb) Values			
	Hb <10.5 g/dL	Hb 10.5 to 12.9 g/dL	Hb >13.0 g/dL	Hb $\geq 13.5$ g/dL
< -1.0 * (or had RBC transfusion within 4 weeks)	↑	↑	No change	Hold, then resume dosing when: Hb <12 g/dL, at a dose that is reduced by one-dose level  Patients are to return weekly to monitor Hb until dosing can be resumed
-1.0 to 1.0	↑	No change	↓	
> 1.0	No change**	↓	↓	

\* A change in Hb from 4 weeks earlier of < -1.0 g/dL means a Hb value that is lower by more than 1.0 g/dL compared to 4 weeks earlier, e.g., a Hb of 9.4 g/dL compared to 10.6 g/dL 4 weeks earlier

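### With TI of at least 56 days and Hb 12.0-12.9 g/dL, Appendix C requires a dose reduction; unless Hb rose by more than 1.0, Appendix D says no change or an increase, and the SAP repeats both

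*Protocol*

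**What the plan says.** **Appendix C, rules for lowering the dose:** "The down titration of the study treatment is allowed at any time but must be performed if any of the following criteria are met". Criterion (a) is TI for at least 56 consecutive days with Hb of 12 g/dL or more. Criterion (b) is the same TI with an Hb rise of at least 2.5 g/dL over 4 weeks. Neither is limited to a phase, except by the appendix heading, "Correction Phase (Prior to Maintenance Phase".

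**Appendix D:** "A modified dose adjustment algorithm will apply to patients who have attained TI" of at least 56 days. Its column for Hb 10.5-12.9 gives an increase after a 4-week fall of more than 1.0 g/dL, no change from -1.0 to 1.0, and a decrease after a rise of more than 1.0. It adds: "The down titration of the dose is allowed at any time".

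**Which appendix applies:**
- The Synopsis sends these patients to Appendix D: "Once TI for at least 8 continuous weeks has been achieved, Maintenance Phase will begin and the study drug dose should follow guidance" there. Sections 2.5 and 3.1 do the same.
- Section 3.3.2 cites both appendices: "Dose reductions can occur at any time per defined criteria".

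**SAP:** Section 10.3 repeats the mandatory criteria without the phase heading and then refers to Section 19.1, which repeats the Appendix D grid.

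**The concern.** Both rules are triggered by 56 days of TI, so they apply to the same patients. For a responder with stable Hb of 12.0-12.9, the plan does not settle whether a reduction is compulsory. For one at 12.0-12.3 after a fall of more than 1.0, one page says reduce and the other says increase.

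The stakes are consistent dosing and patient safety, in a range that begins at the SAP's own safety cut (Hb above 12 g/dL, SAP 14.4). Section 3.3.2 generally does not count dosing outside the algorithm as a deviation, so the deviation tables would not show which rule a site followed. SAP 10.3 also promises a listing of dose changes with the Hb values that meet the adjustment rules. That listing cannot be programmed unambiguously while both rules stand.

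**Working it through.** There is no planned figure to reproduce, so the two rule sets were laid side by side for a patient with ongoing TI of at least 56 days.

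**Inputs.** Appendix C(a): reduce at every Hb of 12.0 or more. Appendix D grid: three rows for the 4-week change, columns 10.5-12.9 and above 13.0, and a hold at 13.5 or more. Range: Hb 12.0 to 13.4 in steps of 0.1, so 15 values × 3 rows = 45 rule cells. C(a) says reduce in all 45.

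**What Appendix D says (number of cells):**

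| Hb (g/dL) | Fall > 1.0 | -1.0 to 1.0 | Rise > 1.0 |
|---|---|---|---|
| 12.0-12.3 | increase (4) | no change (4) | reduce (4) |
| 12.4-12.9 | increase (6) | no change (6) | reduce (6) |
| 13.0 | no column (1) | no column (1) | no column (1) |
| 13.1-13.4 | no change (4) | reduce (4) | reduce (4) |

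**Which cells can be reached.** In 0.1 steps, a fall of more than 1.0 is at least 1.1.
- 12.3 + 1.1 = 13.4, so Hb 12.0-12.3 can be reached without a prior hold, for example 12.2 after 13.3.
- 12.4 + 1.1 = 13.5 and 13.1 + 1.1 = 14.2. Cells at 12.4-12.9 and 13.1-13.4 therefore imply an earlier Hb in the hold column, unless maintenance began within those 4 weeks or the hold had already ended.

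**Count.**
- Opposite directions: 4.
- Mandatory versus optional: 4 + 6 = 10.
- Conflicts in all: 4 + 10 = 14.
- Different on paper but normally under hold: 6 + 4 = 10.
- Undefined: 3.
- Agreement: 4 + 6 + 4 + 4 = 18.
- Check: 14 + 10 + 3 + 18 = 45.

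**Not counted.** C(b) does not contradict D, because a rise of 2.5 or more already meets D's separate reduction rule for a rise above 2.0. The part of D's top row for a transfusion within 4 weeks is also left out, because such a patient does not currently meet C(a).

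**Secondary points.**
- *Column edges:* Hb of exactly 13.0 is in no column, and 13.5 or more meets two.
- *Hold:* Section 3.3.2 allows one hold of at most 2 weeks, whereas D's hold lasts until Hb is below 12, with no time limit. To fit both from 13.5, Hb must fall by more than (13.5 - 12.0)/2 = 0.75 g/dL a week.
- *Appendix C, double-asterisk footnote:* it gives 400 mg for patients of 120 kg or more at Dose Level 3 (2.5 mg/kg; 250 mg above 100 kg), but its marker is on the 3.5 mg/kg cell (350 mg). 400/120 = 3.33 mg/kg is within the cap.
- *250 mg cell, 70-100 kg:* it has no asterisk, yet 250/70 = 3.57 mg/kg, which is 2% above 3.5. The excess ends at 250/3.5 = 71.4 kg. The stated cap overrides the cell.
- *Overdose:* Section 3.3.2 counts a prescribed 400 mg as overdose, while Sections 5.5 and 7.2.2 require the maximum to be exceeded.

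**The case against.** The strongest defence is the phase split. Section 3.3.2 assigns Appendix C to correction and Appendix D to maintenance, and D is a modified algorithm for patients past 56 days. C(a) could then be a check at the transition, with D governing afterwards. This does not hold up. C(a) and C(b) themselves require the 56 days that start maintenance, so a strict split would leave them applying to no one. No text describes a transition check, Section 3.3.2 cites both appendices for reductions, and SAP 10.3 drops the phase label.

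Other points narrow the issue. D permits down titration at any time, so in the stable row a site that reduces satisfies both rules. At 12.0-12.3 after a fall, the earlier Hb was 13.1-13.4, where both rules would normally already have called for a reduction, and Appendix C allows a later increase if response seems to have lessened. That sentence is permissive and does not cancel the requirement to reduce. Sites may ask the monitor or medical monitor about dose, but a site reading only one appendix would see nothing to ask.

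Amendment 03, on which the SAP is based, was not supplied; the Protocol seen is Amendment 02. The SAP itself carries both rules, so the main conflict does not depend on the missing text. The three items on the Appendix C footnote, the 250 mg cell and the overdose wording were seen only in Amendment 02. The cell counts depend on the chosen range and step, and the secondary points are minor.

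**Conclusion.** The concern holds: the dosing rules are wrong as written and should be fixed. Of 45 rule cells at Hb 12.0-13.4, 14 conflict, 10 of them mandatory versus optional and 4 in opposite directions. The documents give no Hb distribution, so the number of patients affected is unknown. The count assumes Hb in 0.1 steps, ongoing TI, and D's hold applied at 13.5 or more.

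The treatment-period endpoints requiring 56 days of TI are essentially unaffected, because the conflict arises only after those 56 days. Any effect on TI of at least 140 days (Test 7 in the SAP's testing sequence) is not quantified.

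**What to change.** By clarification letter or amendment, reconcile Appendix C(a) and (b) with the Appendix D grid, so that one rule applies to each Hb value and Hb change after 56 days of TI. In the same step, settle the column edges at 13.0 and 13.5, and reconcile the 2-week limit with D's hold. Check whether the Appendix C footnote, the 250 mg cell and the Section 3.3.2 overdose wording remain in Amendment 03, and reconcile any that do. Carry the result into SAP 10.3, SAP 19.1 and the dose-adjustment listing. Which rule or dose is right is for the sponsor's clinicians.

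The cost is low: a letter or amendment plus SAP wording. If dosing is complete, one paragraph in the SAP and study report should state which rule was applied.

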10.3. Dose Modification

Dose Escalation

Following commencement of study treatment, patients are evaluated for response after 8 weeks (beginning at Week 9) and, if the patient has required one or more RBC transfusion in that period then the dose is increased by one dose level based on the body weight category. After each dose adjustment, the patient remains on the dose level for a minimum of 8 weeks before further adjustment is permitted based on the next scheduled visit.

Dose Reduction

The down titration of the study treatment is allowed at any time but must be performed if any of the following criteria are met. Hb levels should be retested for confirmation every 2 weeks after a dose reduction; however, it is per investigator's discretion:

- a. Transfusion independent for ≥ 56 days consecutively and Hb ≥ 12 g/dL; or
- b. Transfusion independent for ≥ 56 days consecutively and the rate of rise of Hb ≥ 2.5 g/dL over 4 weeks.
- c. In the instance where the patient achieved TI in the initial 8-weeks of the study, or has undergone treatment with the maximum allowable dose, i.e., 400 mg TIW or 3.5mg/kg for at least 8-weeks, patient may undergo dose reduction by 1-dose level. If there were no difference in erythroid response (same transfusion burden and Hb was unchanged) at this dose level for 8-weeks compared to another lower dose level, investigator may contact Sponsor's Medical Monitor to discuss another potential dose reduction.

Dose adjustment rules for patients who have TI for ≥ 56 Days (Maintenance Phase) can be referenced to [Section 19.1](#).

The number of dose escalations will be summarized descriptively.

The number and percentage of patients who exceed maximum dose will be summarized. The maximum dose of study medication is capped at 3.5 mg/kg per dose or 400 mg, whichever is lower.

The number and percentage of patients with a prescribed dose increase and decrease will be summarized. The number and percentage of patients with an actual dose hold, increase and decrease will be summarized.

The summaries above will be presented by every cumulative 4-weeks, e.g., up to 4 weeks, up to 8 weeks, ..., up to 52 weeks and up to 52 weeks and beyond.

Dose modifications by primary investigator or by patient collected on the eCRF will be listed. Hb level meeting the dose adjustment rules will be combined in the listing.

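### For a patient transfusion-free through the first 8 weeks, Protocol Appendix C and Appendix D give dosing instructions that do not agree, and the boundary between the two appendices is contradictory

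*Protocol*

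**What the plan says.** **Appendix C, Dose Reduction.** The lead-in allows down titration at any time and adds that it "must be performed if any of the following criteria are met". Three criteria follow. Items (a) and (b) require at least 56 consecutive days of TI plus an Hb condition: a level of 12 g/dL or more, or a rise of 2.5 g/dL or more over 4 weeks. Item (c) reads "In the instance where the patient achieved TI in the initial 8-weeks of the study, or has undergone treatment with the maximum allowable dose". It has no Hb condition, and its action is that the patient *may* go down one level.

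**Maintenance.** The Synopsis, Section 3.1 and Section 3.3.2 place the patient in the Maintenance Phase once TI has lasted 8 continuous weeks, and refer to Appendix D for the dose. Appendix D opens "A modified dose adjustment algorithm will apply to patients who have attained TI" for at least 56 days. Its table shows an up arrow at Hb below 10.5 g/dL with a 4-week change between −1.0 and 1.0 g/dL.

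**Escalation text.** Section 3.3.2 says the "starting dose will be maintained if erythroid response (defined as a 50% reduction in pRBC from baseline) is seen after the initial 8 weeks". Appendix C repeats this and adds a Week 12 re-assessment: "if transfusion independence (TI) is observed the dose will not be increased".

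**SAP.** Section 10.3 repeats the reduction list, including "In the instance where the patient achieved TI in the initial 8-weeks of the study", under the same obligatory lead-in. Section 19.1 repeats the Maintenance table. Neither says how the two fit together.

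**The concern.** A site reviewing a patient who was transfusion-free over Days 1–56 can find, for the same visit, a reduction that is either required or optional and an increase. Two sites following the text in good faith could move such patients in opposite directions. Section 3.3.2 says that dosing off the algorithm on clinical grounds is not a protocol deviation, apart from excessive hematopoiesis and overdose, so differing readings would generally not appear as deviations.

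The statistical stake lies after Day 56. Whether TI continues could bear on patient-exposure-weeks of TI (Test 5 in SAP Table 4), change in pRBC (Test 6), TI of 140 days (Test 7) and the exploratory duration of TI. The exploratory analysis of dose requirement by baseline EPO (SAP 12.3.4.5) would also mix drug effect with site reading.

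**Working it through.** No sample-size or power figure is involved. The check follows one patient through the rules.

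**Step 1: timing.** SAP Table 7.1 schedules Week 9 at Day 7 × (9 − 1) + 1 = 57. Protocol Table 2 puts a dose review at that visit. A patient transfusion-free over Days 1–56 therefore has 56 days of TI when reviewed on schedule.

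**Step 2: which rules reach this patient.**
- Appendix C (c) does, by its first limb, whatever the Hb.
- Appendix C (a) and (b) do if their Hb conditions hold, because the 56-day condition is met.
- Appendix D does, because 56 days of TI have been attained.

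**Step 3: actions side by side.**

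| Hb (g/dL) | 4-week change (g/dL) | Appendix C | Appendix D |
|---|---|---|---|
| 9.0, 10.0, 10.4 | 0.0 | (c) reduction | increase |
| 9.0, 10.0, 10.4 | −1.5 | (c) reduction | increase |
| 9.0, 10.0, 10.4 | +1.5 | (c) reduction | no change |
| 10.5, 11.5 | 0.0 | (c) reduction | no change |
| 10.5, 11.5 | −1.5 | (c) reduction | increase |
| 12.0, 12.5 | 0.0 | (c) and (a) reduction | no change |
| 12.0, 12.5 | −1.5 | (c) and (a) reduction | increase |
| 10.5 to 12.5 | +1.5 | (c) reduction, plus (a) from 12.0 | reduction |

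The first two rows and the −1.5 rows at higher Hb point in opposite directions. The rows at 12.0 and 12.5 show a related conflict with item (a), whose wording is not softened by a *may*.

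**Step 4: can the state occur?** Entry requires one central-laboratory screening Hb of 10.0 g/dL or less (Protocol 4.1, criterion 4), so a stable Hb below 10.5 g/dL at Week 9 is reachable.

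**Step 5: is the boundary stated?** The title of Appendix C confines it to the time before Maintenance, and the Synopsis says Maintenance then follows Appendix D. Against that, Appendix C (a) and (b) need 56 days of TI, item (c) needs TI over the first 8 weeks, and Section 3.3.2 lets reductions happen at any time under both appendices.

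**Step 6: Week 12.** The bar on an increase when TI is seen can be read to cover a patient who has been transfusion-free throughout. It would then oppose the Appendix D up arrow. Table 2 lists Weeks 11 and 13 but no Week 12 visit.

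**Step 7: which endpoints are already settled.** SAP 12.3.1 names Days 1 to 56 as a qualifying window, so Test 1 is met before the scheduled review. The same window meets the 52-week and whole-study versions (Tests 2 and 3). Zero transfusions over 8 weeks is a 100% reduction, which meets Test 4.

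**The case against.** The best defence is that the plan does say who governs. After 8 weeks of TI the Synopsis sends the patient to Appendix D, and Appendix C is titled as applying before Maintenance. Item (c) says *may*, both appendices allow down titration at any time, and Appendix C tells sites to call the CRA or medical monitor when in doubt. On that reading Appendix D gives the instruction and item (c) is a permission beside it.

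Much of this stands. It does not remove the *must* over the *may*. It does not explain why Appendix C carries three reduction criteria for patients with 8 weeks of TI if it stops applying there.

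A reader might infer more than the text supports:
- **A clean three-way split of keep, reduce and increase.** The instruction to maintain the starting dose is an exception to an escalation rule triggered by one or more transfusions. A transfusion-free patient never meets that trigger. The Week 12 step fits partial responders at least as well. SAP 10.3, written to Amendment 03, omits the exception; the protocol at hand is Amendment 02.
- **Divergent dosing would go unseen.** SAP 10.3 tabulates dose increases, decreases and holds every 4 weeks, and lists modifications with the Hb that met the adjustment rules. Only the deviation label is missing.
- **Tens of patients are affected.** With 140 patients at exactly 3:2, the roxadustat arm is 140 × 3/5 = 84, and 56% of 84 is about 47. But 56% is a planning rate for any 56-day window in 28 weeks. The documents give neither the share transfusion-free from Day 1 nor the Hb split.

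**Conclusion.** The point holds as a contradiction in the text. For a patient transfusion-free over Days 1–56, Appendix C item (c) is obligatory by its lead-in and optional by its own wording, while Appendix D shows an increase at stable Hb below 10.5 g/dL. Which appendix applies is suggested but contradicted elsewhere. If item (c) is read as optional, a permitted reduction still faces an increase.

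Its size cannot be computed. At the planning rate, 47 roxadustat responders is only a ceiling, reached if every responder were transfusion-free from Day 1, and the Hb conditions would lower it by an unknown amount.

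A reader might also infer a threat to the primary result. The documents do not support that: these patients have responded before the dosing conflict arises. Any effect on later outcomes is possible but unquantified. The conclusion assumes that the dosing text of Amendment 02 carried over; SAP 10.3 and 19.1 show that the reduction list and the Maintenance table did.

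**What to change.** The sponsor's clinical team must reconcile the Synopsis, Section 3.1, Section 3.3.2, Appendix C (Dose Escalation and Dose Reduction) and Appendix D for patients with TI over the first 8 weeks. The reconciled text should answer three questions:

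1. Is item (c) mandatory or optional?
2. Do the Appendix C reductions and the Week 12 rule still operate once Appendix D applies?
3. Which appendix governs from Week 9?

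The related conflict between item (a) and Appendix D at Hb 12.0–12.9 g/dL has the same root and should be settled in the same edit. SAP 10.3 and 19.1 should then carry the agreed wording, so that the planned listing of Hb meeting the adjustment rules has one rule set to apply. No dose or clinical rule is proposed here.

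The cost is a clarification letter or amendment wording and a matching SAP edit, with no added visits, procedures or patients.
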